Assess the effectiveness of different efficacious strategies to decrease the rate of major wound complications following abdominal surgery among high-risk individuals.

Hypotheses

1. Among high-risk patients undergoing abdominal surgery, the use of “small-bites” closure as opposed to “large-bites” closure will increase the proportion of patients who are free of major, chronic wound complications at 1-year post-operative.
2. Among high-risk patients undergoing abdominal surgery, the biologic tissue reinforcement of the suture line as opposed to no reinforcement will increase the proportion of patients who are free of major, chronic wound complications at 1-year post-operative.

Methods

This is a single-institution, 2x2 factorial randomized controlled trial assessing the effectiveness of known efficacious treatments (“small-bites” and tissue reinforcement) among high-risk patients undergoing midline laparotomy or laparoscopic-assisted surgery. [19] Laparoscopic-assisted abdominal surgery is defined as any surgery requiring an open incision in addition to laparoscopy to insert a hand (hand-assisted laparoscopy) or specimen extraction site ≥ 3 cm in

length. This length is chosen because any smaller incision will likely be closed with interrupted sutures rather than running sutures.

Table 1: 2x2 Factorial Design for Prevention of Major, Chronic Wound Complication [19]

		Randomization 1	
		Small-Bites	(Current Care) Large-Bites
Randomization 2	Mesh	Small-Bites Mesh	Large-Bites Mesh
	(Current Care) No Mesh	Small-Bites No Mesh	Large-Bites No Mesh

A 2x2 factorial trial design is utilized because it is more efficient (can assess two interventions simultaneously) and mimics real-world practice (e.g. adoption bundle therapies, adoption of multi-faceted interventions). In addition, the 2x2 factorial design remains novel, particularly among surgical literature that can improve profile of studies performed with this approach.

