Based upon prior studies, it is estimated that the risk of a major, chronic wound complication in this population is at least 30% while either intervention would result in a decrease in relative risk by 30% (i.e. absolute risk reduction from 30% to 20%). The risk of complication at 1 year is the same with open or laparoscopic assisted surgery as shown in multiple prior studies. [1,2,26] Assuming an alpha of 0.05, beta of 0.20, and a dropout rate of 20%, a total of 192 300 patients would need to be enrolled and 154 patients randomized. Based upon our current surgical volume of nearly 6000 general surgical procedures performed each year and our track record of enrolling over 400 surgical patients in the past year for three other trials, we anticipate completing enrollment within one year. To encourage patient follow-up, all patients will be provided with up to a \$10 gift card at the one-year follow-up and \$20 at the three-year follow-up along with payments for their parking (\$10) at both one- and three-year visits. [23]

The primary outcome will be assessed as a categorical variable using a chi square test. In addition, analysis will be performed using a Cochran-Mantel-Haenszel method as well as a multivariate regression analysis accounting for the 2 randomizations and the stratification. Secondary outcomes will be assessed either chi-square or Kruskal-Wallis test.

Based upon traditional Frequentist assessment, if the effect size does not achieve “statistical significance” the conclusions risk being reported as a false negative. To address this potential risk, a more real-world, realistic analysis will be performed using a Bayesian analysis will also be performed. [24,25] The Bayesian models will take the same form as the Frequentist models and include the same covariates. Posterior point estimates, credible intervals, and probability of increase in proportion of patients without hernias or complications will be calculated. Similar models will be used for secondary outcomes. **If interactions or modifiers are identified, then this study will be underpowered and should be considered a pilot study to appropriately power future multi-center randomized controlled trials.**

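### The trial's status as a pilot is made to depend on whether an unspecified interaction is detected, although detection does not determine power

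*Combined protocol and SAP*

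**What the plan says.** The relevant text is in the Statistical analysis section of the combined protocol and SAP.

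- The main test is stated without conditions: "The primary outcome will be assessed as a categorical variable using a chi square test". It is supplemented by a Cochran-Mantel-Haenszel analysis and "a multivariate regression analysis accounting for the 2 randomizations and the stratification". The Bayesian models are to have the same form and covariates as the frequentist ones. No interaction term is named in either.
- The last sentence of the Bayesian paragraph, in bold, reads: "If interactions or modifiers are identified, then this study will be underpowered and should be considered a pilot study". It goes on to give the purpose of such a pilot, which is to power later multi-center trials.
- The design is a 2x2 factorial (Methods), with one hypothesis for small bites and one for mesh (Hypotheses).
- The sample-size statement begins "Assuming an alpha of 0.05, beta of 0.20, and a dropout rate of 20" percent, and ends "a total of 192 300 patients would need to be enrolled and 154 patients randomized". The assumed risks are 30% under current care and 20% with either intervention.

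The plan does not say which interactions or modifiers will be examined, how many, on what scale, in which model, or what p-value or posterior probability counts as identifying one.

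**The concern.** The sentence ties low power to the wrong event. Whether a trial is underpowered follows from its size, the outcome risks and the true effects, all fixed before anyone looks for an interaction. Finding one does not lower the power, and not finding one does not restore it.

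Two errors follow. A chance interaction would relabel the trial as a pilot although nothing about its design had changed. A real interaction would usually be missed at this sample size, and the trial would then escape the label although its limitation is the same. Because the trigger is undefined, two analysts with the same data could also disagree on whether it had been met. Scale alone can decide this: if each intervention independently cut risk by one third, the cells would be 30%, 20%, 20% and 13.3%. That is a departure of 30 − 20 − 20 + 13.3 = 3.3 points from additivity on the risk-difference scale and no interaction on the risk-ratio scale.

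At stake is how readers are told to treat the answers to both hypotheses.

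**Working it through.** **Inputs.** From the Statistical analysis section: risks 30% and 20%, alpha 0.05, power 80%, dropout 20%, and the figures 154, 192 and 300. Assumed because not stated: two-sided alpha and equal allocation (N/2 per margin, N/4 per cell). Evaluable totals used are 154 as printed, 300 as printed, and 300 × 0.8 = 240.

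**Step 1: the plan's sample size.** For two proportions (pooled chi-square formula), with mean risk 0.25:

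n per arm = [1.960·√(2 × 0.25 × 0.75) + 0.842·√(0.30 × 0.70 + 0.20 × 0.80)]² / 0.10² ≈ 293.2, rounded up to 294.

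This gives 588 in total, or 588/0.8 = 735 after dropout. One-sided, the total is 462; with a continuity correction (two-sided), 626. A 30% relative reduction from 30% is strictly 21%, and that needs 734, or 918 after dropout. None of these variants gives 154, 192 or 300. Only the dropout step links two of the printed figures: 154/0.8 = 192.5.

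**Step 2: main-effect power, 30% versus 20%.** Power ≈ Φ[(0.10 − 1.960·SE₀)/SE₁], where SE₀ = √(2 × 0.25 × 0.75/n), SE₁ = √((0.21 + 0.16)/n) and n = N/2.

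| Evaluable N | SE₀ | SE₁ | Power |
|---|---|---|---|
| 154 | 0.0698 | 0.0693 | 30% |
| 240 | 0.0559 | 0.0555 | 43% |
| 300 | 0.0500 | 0.0497 | 52% |

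With 21% in place of 20%, power is 25%, 36% and 43%. No term in the formula refers to the result of an interaction test.

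**Step 3: power to detect an interaction.** Take an interaction as large as the planned main effect: neither, small bites only, mesh only and both at 30%, 20%, 20% and 20%. The contrast is 0.30 − 0.20 − 0.20 + 0.20 = 0.10. Its standard error is √[(0.21 + 3 × 0.16)/(N/4)] = √(0.69 × 4/N). Power ≈ Φ(0.10/SE − 1.960) + Φ(−0.10/SE − 1.960).

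| Evaluable N | SE | 0.10/SE | Power |
|---|---|---|---|
| 154 | 0.134 | 0.75 | 12% |
| 240 | 0.107 | 0.93 | 15% |
| 300 | 0.096 | 1.04 | 18% |

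On the logit scale the same cells give 11%, 14% and 16%. For 80% power on the risk-difference scale, N = 4 × 0.69 × (1.960 + 0.842)²/0.10², or about 2,167 evaluable patients, against 588 for the main effect.

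**Step 4: false triggers.** If no interaction exists, one test at 0.05 identifies one in about 5% of trials; a simulation of the logit test gave about 4% to 5%. With k independent tests the chance is 1 − 0.95^k, which rises with k. The plan gives no k.

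**Step 5: what a true interaction does.** With the Step 3 cells, each marginal comparison is (30 + 20)/2 = 25% against (20 + 20)/2 = 20%. Marginal power is then about 11%, 15% and 18% at N = 154, 240 and 300. The loss comes from the interaction existing, whether or not a test detects it.

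**The case against.** The best defence is that the sentence is a clumsy but cautious factorial caveat. If small bites and mesh are not additive, the marginal effects are harder to interpret, the trial is too small, and a larger one is needed. Read to its end, the sentence points that way, and Step 5 supports it in substance: a true interaction of this kind cuts marginal power from 30–52% to 11–18%. That part stands. It does not rescue the wording, because the condition is that an interaction is identified, and at 12% to 18% power identification is a poor guide to existence. It also leaves modifiers other than the partner treatment undefined.

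Three stronger readings are tempting, and the documents do not support them.

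- A reader might infer that the rule decides whether the primary result counts. It does not: the chi-square, Cochran-Mantel-Haenszel, regression and Bayesian analyses are prescribed without condition. Only the classification of the study changes.
- A reader might call the set of triggering tests unlimited and attach a large error rate. Adding surgical approach and the five high-risk criteria, each crossed with both treatments, to the one factorial interaction makes 13 tests and 1 − 0.95^13 = 49%. But the plan does not name these as modifiers to be tested; the five criteria are eligibility rules. The accurate word is unspecified.
- A reader might suspect a device for setting aside an unwelcome result. Nothing in the text shows such an intent.

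It is also fair to say that the regression is described by its factors and not by a full equation, so an interaction term is unspecified and not excluded. Finally, the sentence is the plan's one explicit acknowledgement of limited power, so deleting it without a replacement would lose a useful caution.

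**Conclusion.** The concern holds as a defect in how the trial's status is determined. The rule makes a pilot label conditional on detecting an undefined interaction, while the low power it warns of is present in any case: about 30% to 52% for the main effects across 154 to 300 evaluable patients. The detection step is weak in one direction, with 12% to 18% power for a 10-point interaction, and in the other direction it gives a chance trigger in about 5% of trials for a single test at 0.05, more if further modifiers are tested.

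These sizes rest on two-sided alpha, equal allocation, the plan's 30% and 20%, and the illustrative cells 30/20/20/20%. The sample size cannot be reproduced and its printed figures need reconciling; that is a separate matter, and the range used here covers the totals they imply. The point does not invalidate the data or the primary analyses. It should be corrected before analysis.

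**What to change.** Replace the conditional sentence with provisions that do not depend on the results:

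1. An unconditional limitation giving the actual power for each main effect at the expected evaluable number, and stating that power to detect or rule out an interaction is low.
2. One prespecified interaction, small bites by mesh, with its model stated. Report the estimate and 95% interval on the risk-difference and odds-ratio scales, together with the four cell rates. The cell rates are useful in their own right, since the Methods section justifies the factorial design partly because it "mimics real-world practice (e.g. adoption bundle therapies, adoption of multi-faceted interventions").
3. The marginal comparisons kept as the primary analysis whatever the interaction estimate shows, and interpreted alongside the cell rates.
4. All other modifier analyses labelled exploratory, with no bearing on how the trial is classed.

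The cost is SAP wording, slightly more reporting, and a less favourable stated power. No patients, visits or data are added.
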